#### **Post-tele-visit**

- Participant Preference and Burden Survey. Following completion of the visit, participants will be emailed a direct link to REDCap to complete this survey.

#### *Smartphone Application Registration:*

The study team member will initiate the registration process by inputting the participant's GUID, smartphone number and visit date into Sage Bionetworks Synapse web portal a couple of days before the participants orientation visit. This will create a mPower account for the participants in the Sage Bionetworks Bridge service. During the baseline tele-visit the study team member will help the participants to download and install the application. After installation, the study team member will review proper performance of each task and direct the participant towards helpful resources in the event that they have any further questions about the tasks. A study team member will remotely supervise the participant while he/she completes a complete set of smartphone tasks.

#### d. Smartphone Sessions (Baseline, Month 3, 6, 9, 12, 15, 18, 21, 24)

- 14-day smartphone sessions will occur on a quarterly basis.
- Given diurnal variation in active task performance, participants will be asked to select morning or afternoon as their preferred window for completion and to consistently attempt to complete the active tasks according to their selected preference.
- Participants will be notified one day before the start of each 14-day session

During these 14-day sessions, participants will be asked to complete daily 4 to 6-minute smartphone-based motor tasks. If they fall behind and are not able to complete at least 10 daily activity sets they can optionally continue for up to 5 additional days.

The following motor activities will be completed by the participant:

- Gait Task
- Finger Tapping Task
- Resting Tremor Task

- Balance task

During these 14-day sessions, participants will be asked to complete an approximately 8-minute set of smartphone-based cognitive assessments on at least 3 of the days.

The following activities will be completed by the participant:

- Digit Span
- Digit Symbol Substitution Tests
- Spatial Working Memory

Participants will be asked to provide basic demographic information through the application once. Participants will also use the application to track their medication adherence relative to tasks and, optionally, self-reported symptoms and triggers. Additionally, participants may perform the active tasks at any time outside of the 14-day smartphone sessions if desired.

Compliance will be actively monitored.

- Participants will receive reminders if they do not perform the activities for two consecutive days and/or after not performing the activities for four days of the 14-day session.
- Participants who enable notifications will receive daily notifications during each 14-day session
- Sage Bionetworks will make quarterly reports available to CHeT/CTCC that will include each participant's compliance status.

e. FI Sessions (Baseline, Month 3, 6, 9, 12, 15, 21, 24)

- AT-HOME PD participants will be asked to complete a set of standard questionnaires through a companion study called FI, (<https://foxinsight.michaeljfox.org>).
- Participants will be asked to complete the questionnaires in the SOA every 90 days. [Refer to SOA] The baseline visit takes approximately one hour to complete; subsequent visits take only 10-15 minutes to complete.
- Participants will have a 90-day window in which to complete the questionnaires. However, they will be encouraged to complete the Baseline, Month 12, and Month 24 FI questionnaires within 28 days of the corresponding tele-visit.

Compliance will be actively monitored.

- Those participants that fail to complete all of the assessments will be sent an email reminder by FI after approximately 45 days.
- FI will send another email reminder after approximately 88 days if all of the assessments still have not been completed.
- FI will send quarterly reports to CHeT/CTCC that will include each participant's compliance status. This will continue until a publicly-accessible FI research database is available through LONI.

#### f. Premature Withdrawal Visit

Premature withdrawal will be defined as withdrawal from the tele-visit component (or the full study) prior to completion of the month 24 tele-visit. Participants have the right to withdraw from the study, or any individual component of the study, at any time without prejudice. Although not anticipated, an investigator may withdraw a participant from the study if participation places the participant at undue risk or if the participant dies or experiences another reportable event that precludes further study participation. In all other circumstances, all participants should be retained in the study regardless of compliance to limit bias from informative drop-out.

In the event of premature withdrawal from the study, the Premature Withdrawal (PW) Visit procedures and evaluations should be completed whenever possible whether or not the withdrawal is determined at a regularly scheduled study visit or at an unscheduled visit.

Reasons for withdrawal of the participant prior to completion of the study must be stated in the eCRF for all study participants who were enrolled in the study.

The premature withdrawal tele-visit is expected to take approximately 60 minutes to complete.

Pre-tele-visit – up to one week prior to each visit, participants will be emailed the direct links to the following REDCap surveys, which will need to be completed before the tele-visit.

- MDS-UPDRS parts 1b and 2.
- Self-Reported Fall Questionnaire
- Patient Global Impression (PGI)-Severity. PGI-Change will be completed during month 12 and month 24 visits only.

The following assessments will be completed during the tele-visit:

- Review Reportable Events
- Review Concomitant Medications
- MDS-UPDRS parts 1a, 3 and 4 (where applicable). Part 4 will only be completed for individuals who are receiving dopaminergic therapy.
- Montreal Cognitive Assessment (MoCA)
- Modified Schwab & England Activities of Daily Living Scale (SEADL)
- Clinical Global Impression (CGI)-Severity. CGI-Change will be completed during month 12 and month 24 visits only.
- Determination of Falls
- Confirmation of participant completion of MDS-UPDRS parts 1b and 2, self-reported falls assessment, and PGI-severity and change

- Review of participant compliance with smartphone tasks and FI patient-reported outcome measures where applicable
- Smartphone application registration and orientation, where applicable, will occur during the baseline tele-visit (see below).
- Completion of a complete set of smartphone active motor and cognitive tasks (where applicable)
- Early termination survey

#### Post tele-visit

- Participant Preference and Burden Survey. Following completion of the visit, participants will be emailed a direct link to REDCap to complete this survey.

### g. Passive Data Collection

For participants that optionally consent to passive data collection, the smartphone application will collect multiple streams of passive data: movement patterns captured by location services (including GPS) and motor activity patterns captured by accelerometers and gyroscopes. To reduce issues relating to patient privacy concerns, movement patterns will be collected using displacement vectors without storing actual GPS coordinates. To reduce burden relating to use of data plans for data transfer, the application will transfer data on a daily basis and preferably using a Wi-Fi connection. In order to ensure that monitoring is naturalistic, participants will not be given any instructions regarding how or when to carry their smartphone.

#### 5.5.1 Sub-study Study Visits

##### a. Pre-Screen

The Pre-Screen will be conducted via telephone or during a potential participant's SUPER-PD study visit by an AT-HOME PD team member. It is expected to take approximately 10-15 minutes to complete.

The following activities will be completed:

- Overview of the study and assessment of interest

If the individual is interested in participating:

- Pre-screen questionnaire for eligibility
- eConsent (link to REDCap emailed)

##### b. Tele-Visit (within 14 days of SUPER-PD baseline or month 12 study visit)

- The tele-visit will be conducted remotely using a web-based video platform and is expected to take approximately 30 minutes to complete.

- For participants on symptomatic dopaminergic therapy, the Movement Disorder Society – Unified Parkinson Disease Rating Scale (MDS-UPDRS) part 3 will be obtained in the usual ON state. The timing of last dopaminergic medication intake will be recorded.

The following assessments will be completed during the tele-visit:

- Verify eligibility and eConsent
- MDS-UPDRS part 3
- Montreal Cognitive Assessment (MoCA)
- Reportable Events

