Data Management	
Data collected during tele-visits will be entered and maintained in REDCap (a secure web-based survey and data management system). Each participant’s baseline demographic information, concomitant medications, and health history as well as clinical data including PD-PROP from the corresponding SUPER-PD visit, will be transferred from the SUPER-PD REDCap project to the AHPD sub-study REDCap project. All data will ultimately be transferred to Synapse (an open source collaborative platform) for analysis. For any sub-study participants who are participating in the mPower 2.0 component of SUPER-PD, their smartphone data from the corresponding SUPER-PD visit and associated remote 2-week burst will be linked with AT-HOME PD data within Synapse.
 
From Synapse, the cleaned, processed, and event date- and time-transformed dataset will be transferred to the PDBP’s Data Management Resource for further distribution to PDBP investigators and will be made available to the wider research community through their qualified researchers program.

Statistical Analysis	Paired MDS-UPDRS and MoCA scores from in-person and TV assessments of SUPER-PD participants will be pooled with data from SURE-PD3. The accuracy of predicted in-clinic scores based

	
on TV assessments using calibrations from REACT-PD will be summarized by Lin's concordance correlation coefficient, <math>r_c</math>, equivalent to an intra-class correlation (ICC). The REACT-PD calibrations will be judged sufficiently accurate if <math>r_c > 0.8</math>. If we observe insufficient concordance, we will re-calibrate using all available data from REACT-PD, SURE-PD3, and SUPER-PD.

Sample Size	
With a combined sample size of ~60 SURE-PD3 and SUPER-PD participants expected to complete at least one TV close in time to their in-person clinic visit, the study will have 80% power to conclude that the REACT-PD calibrated tele-visit estimates are sufficiently accurate (<math>r_c > 0.8</math> at alpha = 0.05) if the true concordance is at least 0.89.

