**Table 3: AHPD - SUPER-PD Cohort Schedule of Activities (SOA)**

	Pre-Screen Contact (TC or in-person)*	Baseline Tele-Visit (±14 days of SUPER-PD baseline or month 12 visit)
Pre-Screening Questionnaire	X	
eConsent	X	
Verify Eligibility		X
Verify Consent		X
Reportable Events		X
MoCA		X
MDS-UPDRS part 3		X

\*May occur either in-person (at time of their SUPER-PD visit) or by phone

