All SURE-PD3 participants who have not yet (or have recently) completed their participation in SURE-PD3 should have their baseline tele-visit after their final in-person study visit (or equivalent) in the planned treatment period. Ideally, this baseline tele-visit will occur within 28 days of the final in-person study visit (or equivalent) in the planned wash-out period to allow validation of tele-visit data acquisition versus that of the standard in-office visits. The baseline visit will occur within 0-60 days of the screening visit.

- All of the tele-visits will be conducted remotely using a web-based video platform and are expected to take approximately 60-90 minutes to complete.
- All of the tele-visits will consistently be attempted to be conducted in either the morning or the afternoon, according to participant preference, to reduce the effect of diurnal symptom variation. For participants on symptomatic dopaminergic therapy, the Movement Disorder Society – Unified Parkinson Disease Rating Scale (MDS-UPDRS) part 3 will be obtained in the usual ON state. The timing of last dopaminergic medication intake will be recorded.
- A +/- 28-day window (from baseline TV) will be used for the Month 12 and Month 24 visits, however, visits should ideally be scheduled such that they are conducted during the corresponding 14-day smartphone session.

**Pre-tele-visit** – Up to one week prior to each visit, participants will be emailed the direct links to the following REDCap surveys, which will need to be completed before the tele-visit.

- MDS-UPDRS parts 1b and 2.
- Self-Reported Fall Questionnaire
- Patient Global Impression (PGI)-Severity. PGI-Change will be completed during month 12 and month 24 visits only.

The following assessments will be completed during the tele-visit:

- Review Reportable Events
- Review Concomitant Medications
- MDS-UPDRS parts 1a, 3 and 4 (where applicable). Part 4 will only be completed for individuals who are receiving dopaminergic therapy.
- Montreal Cognitive Assessment (MoCA)
- Modified Schwab & England Activities of Daily Living Scale (SEADL)

- Clinical Global Impression (CGI)-Severity. CGI-Change will be completed during month 12 and month 24 visits only.
- Determination of Falls
- Confirmation of participant completion of MDS-UPDRS parts 1b and 2, self-reported falls assessment, and PGI-severity and change
- Review of participant compliance with smartphone tasks and FI patient-reported outcome measures where applicable

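### The SUPER-PD sub-study does not match its tele-visit to the paired in-person visit on time of day and does not review medication at the tele-visit, so true symptom change between the two ratings lowers r_c and cannot be told apart from tele-visit error

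*Combined protocol and SAP*

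**What the plan says.** The sub-study synopsis gives one objective, the cross-sectional reliability of tele-visit against in-person assessment, with MDS-UPDRS part 3 and MoCA as outcomes. Three places set the conditions of the tele-visit:

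- Table 3 heads its only visit column "Baseline Tele-Visit (±14 days of SUPER-PD baseline or month 12 visit" and lists eligibility, consent, reportable events, MoCA and part 3. Concomitant medications are not listed.
- Section 3.1.1 repeats the 14-day window.
- Section 5.5.1 b states "The tele-visit will be conducted remotely using a web-based video platform and is expected to take approximately 30 minutes to complete". For treated participants it adds "part 3 will be obtained in the usual ON state. The timing of last dopaminergic medication intake will be recorded".

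None of these refers to the time of day of the in-person visit. The synopsis (Data Management) takes "concomitant medications, and health history as well as clinical data including PD-PROP from the corresponding SUPER-PD visit" into the sub-study REDCap project. Section 10.1 says that all concomitant medications will be recorded.

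In the main study, Section 5.5 c keeps each participant's tele-visits in one half of the day, "according to participant preference, to reduce the effect of diurnal symptom variation". Section 5.5 b asks for the same window for smartphone tasks, and Section 1.1 reports fluctuation linked to levodopa dosing and to time of day.

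On size, the synopsis says: "With a combined sample size of ~60 SURE-PD3 and SUPER-PD participants" who complete a tele-visit near their clinic visit, "the study will have 80% power to conclude that the REACT-PD calibrated tele-visit estimates are sufficiently accurate" (r_c above 0.8, alpha 0.05) if the true concordance is at least 0.89.

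**The concern.** An agreement study should hold the patient's state as constant as it reasonably can, so that what remains is the effect of rating by video. Here a participant rated in person in the morning may be rated by video in the afternoon, up to two weeks before or after. A change of dopaminergic regimen in between would have no planned record at the tele-visit.

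Lin's r_c cannot distinguish a patient who has changed from a rater who disagrees. If r_c falls short, Section 13.2 investigates bias, scale difference and imprecision and then recalibrates. Its calibration matches means and standard deviations. Once those agree, r_c equals the ordinary correlation, which no rescaling can raise, so noise from the patient's state would remain. A sound tele-visit method could be judged insufficient, and the data would not show why.

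A separate matter works in the other direction. In-person clinical data go into the same REDCap project as the tele-visit data, and nothing says when. If the tele-visit rater could see the in-person score, r_c would tend to be too high.

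**Working it through.** **Inputs.** From the sub-study synopsis and Section 13.4: about 60 pairs (about 10 SURE-PD3 plus about 50 SUPER-PD), threshold 0.80, true r_c 0.89, alpha 0.05 with sidedness not stated, power 80%. The variance added by unmatched conditions is not in the documents. It is an assumption, written f, as a share of the variance of a matched score.

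**Step 1: the plan's figure.** Fisher z: power = Φ[(atanh r_c − atanh 0.80) × √(n − 3) − z].

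- atanh 0.89 = 1.4219 and atanh 0.80 = 1.0986; the difference is 0.3233.
- 0.3233 × √57 = 0.3233 × 7.550 = 2.441.
- One-sided: Φ(2.441 − 1.645) = Φ(0.796) = 78.7%.
- Two-sided: Φ(2.441 − 1.960) = Φ(0.481) = 68.5%.

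The stated 80% therefore reproduces as a one-sided test, with no margin to spare.

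**Step 2: illustration of mismatch.** Let matched pairs have equal means and unit variance, 0.89 stable and 0.11 error. Independent state variation f at each visit gives r_c = 0.89/(1 + f). For f = 0.02, r_c = 0.89/1.02 = 0.8725, atanh = 1.3437, and Φ(0.2451 × 7.550 − 1.645) = Φ(0.205) = 58%.

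| f | r_c | One-sided power, 60 pairs |
|---|---|---|
| 0 | 0.890 | 78.7% |
| 0.02 | 0.873 | 58% |
| 0.05 | 0.848 | 30% |
| 0.08 | 0.824 | 13% |
| 0.10 | 0.809 | 7% |
| 0.1125 | 0.800 | 5% |

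If the rule is read as the point estimate alone exceeding 0.8, simulated pass rates (20,000 replicates) are 99%, 86% and 56% at f = 0, 0.05 and 0.10.

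**Step 3: not every pair need be mismatched.** If f = 0.10 applied to half the pairs, the average added variance is 0.05. By the same approximation r_c is about 0.85 and power about 30%, not 7%.

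**Step 4: what could be separated afterwards.**

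| Item | Sub-study tele-visit | Paired SUPER-PD rating |
|---|---|---|
| Clock time | Stored with the record (15.5) | Not stated |
| Medication state | Usual ON (5.5.1 b) | Not stated |
| Time of last dose | Recorded (5.5.1 b) | Not stated |
| Concomitant medications | Not in Table 3 | Transferred from SUPER-PD |

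Each row is documented on one side only, so these documents do not secure a paired comparison of state.

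**The case against.** Several counter-arguments are sound, and they rule out stronger readings.

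- A reader might infer that the main study applies a control that the sub-study drops. It does not. The half-day rule aligns a participant's tele-visits with each other and with the smartphone tasks, and matches none of them to an in-person visit. The SURE-PD3 validation pairs share the half-day gap. They do have a medication review at the tele-visit (Table 1).
- A reader might infer that medication state is uncontrolled. Section 5.5.1 b requires the usual ON state and records last-dose time, as in the main study. What is missing is any tie to the in-person rating and any record of a regimen change.
- A reader might take the power losses as an estimate. The plan's 0.89 may already allow for ordinary fluctuation between nearby visits, in which case Step 2 subtracts it twice. Nor is every pair necessarily mismatched. The table shows sensitivity only.
- Rater sight of the in-person scores is possible but not shown. The synopsis does not name part 3 or MoCA scores among the transferred items and gives no transfer date. The tele-visit may come first, and Section 17.2 limits data access by user ID.
- The SUPER-PD protocol, the Operations Manual and the separate SAP are not available here and may set matching rules. If they do, a cross-reference would close most of the point.

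The 14-day window is also no wider than the 2 to 4 weeks used in REACT-PD (Section 1.2). That limits the problem without removing it: time of day and a dose change can differ within any such window.

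**Conclusion.** The concern holds as a gap in design and recording. The sub-study's one purpose is paired agreement. Its documents do not match the pair on time of day, do not review medication at the tele-visit, and do not link the recorded ON state and dose timing to the in-person rating. Table 3 also sits uneasily with Section 10.1.

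Unmatched state lowers r_c and so works against accepting tele-visits. The illustrative range is r_c 0.87 to 0.81 and power 58% to 7%, against about 79% for matched pairs. It assumes that 0.89 describes matched pairs, that independent variation is added at both visits in every pair, and that f is 2% to 10%. The true size cannot be derived from the documents. Unblinded rating, if it occurred, would act in the opposite direction and should be kept as a separate point.

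This does not invalidate the sub-study. It is a low-cost improvement, best made before visits take place, because state information not collected at the visit may not be recoverable.

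**What to change.** In Section 5.5.1 b and Table 3:

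1. Book the tele-visit, where possible, in the same half-day as the paired SUPER-PD visit.
2. Hold clock time and time since last usual dopaminergic dose for both ratings.
3. Add one question on whether dopaminergic medication changed between the two visits. This also reconciles Table 3 with Section 10.1.
4. Keep all pairs in the primary r_c, as Section 13.5 requires. Pre-specify a sensitivity analysis restricted to pairs rated in the same half-day with no medication change. Making that subset primary would conflict with Section 13.5 and would select the more stable pairs.
5. Release the in-person part 3 and MoCA scores to the sub-study REDCap project only after the tele-visit scores are entered and locked.

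If the Operations Manual or the SUPER-PD protocol already covers any of this, cite it here.

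The cost is slightly less scheduling flexibility, one added question, a few timing fields and a short delay in data transfer. Treatment is unaffected.

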## 6. ASSESSMENTS

### 6.1 Primary Assessments

#### a. Pre-Screening Questionnaire

The pre-screening questionnaire includes questions regarding access to an internet-enabled device that will support participation in tele-visits, possession of a web-camera, and possession of a suitable smartphone.

#### b. Technology Survey

Survey questions were originally adapted from the Pew Internet & American Life Project Question database. The survey includes questions regarding access and use of specific technology and prior experience with tele-visits.

#### c. Movement Disorders Society Unified PD Rating Scale (MDS-UPDRS)

The MDS-UPDRS will be conducted per the Schedule of Activities. The MDS-UPDRS was designed by movement disorders experts to address weaknesses of the original UPDRS (e.g., by adding questions on constipation and sialorrhea) while preserving its overall format. The MDS-UPDRS has four parts:

- **Part I (non-motor experiences of daily living)**, comprising
  - Part Ia concerning behaviors that are assessed by the CHeT Site Investigator with all pertinent information from patients and caregivers
  - Part Ib that is completed by the patient with or without the aid of the caregiver, but independently of the Investigator.
- **Part II (motor experiences of daily living)**, designed to be a self-administered questionnaire like Part Ib, but similarly can be reviewed by the study team to ensure completeness and clarity.

- **Part III (motor examination)** has instructions for the rater to give or demonstrate to the patient; it is completed by the clinician rater. Given the remote nature of our evaluations, we will administer a modified version of part III that does not include assessment of rigidity or postural instability.
- **Part IV (motor complications)** with instructions for the rater and also instructions to be read to the patient. This part integrates patient-derived information with the rater's clinical observations and judgments and is completed by the rater. **Complete Part IV only if ST has been initiated.**

Participants will self-administer Parts Ib and II, through completion of REDCap surveys, but the study team member will review responses for completion and ask the participant to complete it during the tele-visit if incomplete. Use of MDS-UPDRS is responsive to core instrument recommendations for the Quality of Life subdomain of the National Institute of Neurological Disorders and Stroke (NINDS) Common Data Elements (CDEs) for PD, and to the Food and Drug Administration (FDA) guidance encouraging use of PROs as a substantial portion of the responses are patient-reported. The investigators are neurologists or board-certified nurse practitioners who have received formal MDS-UPDRS certification (by the MDS) and will have additionally undergone joint training to reconcile scoring differences and minimize inter-rater variability.

**Ideally, the same Site Investigator should assess all participants on parts Ia, III, and IV (when applicable) of the MDS-UPDRS at all study visits.**

D. Montreal Cognitive Assessment (MoCA)

In early PD, when cognitive deficits occur, they are subtle and mild, and the participants usually perform in the normal range of the widely used Mini-Mental State Exam (MMSE). The MoCA is a rapid screening instrument like the MMSE but was developed to be more sensitive to patients presenting mild cognitive complaints. It is designated an NINDS CDE for PD. The MoCA assesses short-term and working memory, visual-spatial abilities, executive function, attention, concentration, language and orientation. As completion of the MoCA requires performance of some tasks on paper, the participant will be sent a copy of the relevant portions of the MoCA (trail-making, cube copying) prior to the tele-visit. Ideally, this will be sent in a sealed envelope and the participant will be asked to open the envelope only during their tele-visit. However, it may alternatively be sent via email with instructions to print immediately prior to the tele-visit. During the tele-visit, the participant will be instructed on how to complete these tasks and will be asked to display their responses such that they can be visualized and evaluated by the study team member. The total score ranges from 0 to 30 (highest function).

E. Modified Schwab and England Activities of Daily Living Scale (SEADL)

The SEADL is an Investigator and participant assessment of the participant's level of independence. The participant will be scored on a percentage scale reflective of his/her ability to perform acts of daily living. Printed scores with associated descriptors range from 100% to 0% in increments of 10%, where 100% is "participant has full ability and is completely independent; essentially normal" and 0% is "vegetative functions such as swallowing, bladder and bowel functions are not functioning; bedridden". Scores should be coded in increments of 10, (i.e. 090, 080, 070). This assessment will be completed jointly by the participant and Investigator.

F. Clinical Global Impression and Patient Global Impression Scales (CGI)

The CGI is an observer-rated scale that measures illness severity (CGIS) and global improvement of change (CGIC). Each component of the CGI is rated separately; the instrument does not yield a global score.

The CGIS is rated on a 7-point scale, with the severity of illness scale using a range of responses from 1 (normal) through to 7 (amongst the most severely ill patients). CGIC scores range from 1 (very much improved) to 7 (very much worse).

Similarly, the PGI is a patient-rated scale that measures illness severity (PGIS) and global improvement of change (PGIC).

g. Falls Assessment

Falls will be assessed using two questionnaires, which have been incorporated into an on-going large prospective study (PPMI). The self-reported falls assessment is a 1-item questionnaire that will be completed by the participant. The determination of falls assessment, which will be completed by the investigator, includes questions about freezing of gait and falls over two time periods (the past week and the past 12 months).

